4.3.2 Secondary Efficacy Variables

$AOB_{0.5}$, $AOB_{0.1}$, $AOB_{0.3}$, $AOB_{0.6}$, $AOB_{0.9}$: AOB for 0.5, 1, 3, 6 and 9 hours will be defined and analyzed in a similar manner as $AOB_{0.12}$ in section 4.3.1. However, no adjustments for multiple testing will be carried out. The ANOVA tables for $AOB_{0.5}$, $AOB_{0.1}$, $AOB_{0.3}$, $AOB_{0.6}$, and $AOB_{0.9}$ will be tabulated in Table 9. Adjusted means, standard errors, and 95% confidence intervals for $AOB_{0.5}$, $AOB_{0.1}$, $AOB_{0.3}$, $AOB_{0.6}$, $AOB_{0.9}$ will be tabulated by treatment in Table 10. For differences in $AOB_{0.12}$ between Super Poligrip Free and no adhesive, Experimental Denture Adhesive 1 and no adhesive, and Experimental Denture Adhesive 2 and no adhesive, adjusted differences, standard errors, and 95% confidence intervals will be tabulated in Table 8.

Subject-level profile plots (connected scatter plots, spa) of $AOB_{0.5}$, $AOB_{0.1}$, $AOB_{0.3}$, $AOB_{0.6}$, $AOB_{0.9}$, and $AOB_{0.12}$, with all treatments overlayed on the same figure will be plotted by subject in Figure 3.

Adjusted bite force means over time at 0, 0.5, 1, 3, 6, 9, and 12 hours by treatment will be tabulated in Table 12 and plotted in Figure 1. The adjusted means will come from a repeated measures ANCOVA model. Bite force at each time will be the outcome. Fixed effects will be study period, treatment, time, period-by-time interaction, and treatment-by-time interaction. The covariate is the subject level baseline. Subject will be included as a random effect. Time within study period will be included as a repeated factor, with an unstructured variance/covariance matrix. If the repeated measures ANCOVA model is unable to converge, the analysis will be split into separate analyses for each time point: time 0 will use analysis of variance with treatment and period as fixed effects and subject as a random effect; subsequent time points will use ANCOVA with treatment and period as fixed effects, subject as a random effect, and subject-level baseline as the covariate. No statistical comparisons will be taken from this analysis; the purpose of the model is only to generate the adjusted means and standard errors.

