2.2 Background

A BF transducer will be used to measure the maxillary incisal bite force over a 12-hour time period. BF indicates denture retention by measuring the maximum force that can be applied by the incisors prior to dislodgement of the maxillary denture (Munoz et al., 2012). This is line with previous GSK studies CCI

) where the BF clinical model has been successfully used to demonstrate the efficacy of denture adhesives to improve denture hold for up to 12 hours and as early as 30 mins after adhesive application, whilst also demonstrating differences in strength among various adhesive formulations.

Based upon their compositions and pre-clinical *in vitro* testing methodology, the two experimental adhesives are expected to provide sufficient hold to meet the objectives of this study. Both share similarities with the positive control adhesive which has previously been shown to be effective in this clinical design (CCI [REDACTED])

[REDACTED]).

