2.4 Mechanism of Action/Indication

Denture adhesives function by forming an adhesive layer between the denture and gum surface thereby reducing denture movement and improving hold. These adhesive properties are driven by a combination of different adhesive polymers in the adhesive creams, including carboxymethyl cellulose (CMC), carbomer and polyvinyl methyl ether/maleic anhydride co-polymer. The polymers are dispersed in a hydrocarbon medium as a cream. In the oral cavity, the cream absorbs water and the polymers hydrate providing adhesiveness between the denture and the denture bearing tissues.

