4.3.1 Primary Efficacy Endpoint

4.3.1.1 Primary Efficacy Endpoint Definition

Incisal bite force (BF) (lbs) will be recorded at hour 0 (baseline, pre-treatment) and at 0.5, 1, 3, 6, 9, and 12 hours post-treatment.

The primary efficacy endpoint is area over baseline (AOB) over 12 hours for BF (denoted by AOB_{0-12}) for each adhesive.

To calculate AOB_{0-12} , first the AUC is calculated from 0 to 12 hours using the trapezoid method using the nominal bite force times; we denote this by AUC_{0-12} . AOB_{0-12} is defined as $(AUC_{0-12})/12$ minus baseline BF. This transformation will return the measurement to the same scale as the original observations whilst also looking at the average amount of improved force over time by subtracting the baseline value. Higher values of AOB demonstrate a stronger BF over time than lower values. Missing readings will be imputed using linear interpolation between pre and post the missing values, if necessary. In the case of more than one missing value or if the 12-hour value is missing, the AOB will be set to missing.

The study validity will first be evaluated by comparing Super Poligrip Free vs no adhesive for AOB_{0-12} . Demonstrating study validity ($p<0.05$ for Super Poligrip Free vs no adhesive) is a prerequisite to making inferences for all other treatment comparisons. If the initial validation step is not achieved, the other treatment comparisons will still be performed and presented but the significance tests will not be formally evaluated. The primary objectives are to compare AOB_{0-12} of the two test experimental adhesives versus no adhesive. Therefore, study success is defined as achieving both (a) study validity (Super Poligrip Free superior to no adhesive) and (b) superiority of Experimental Denture Adhesive 1 compared to no adhesive, or Experimental Denture Adhesive 2 compared to no adhesive, or both.

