4.4.4 Oral Hard Tissue Examination

Oral hard tissue exam (OHTE) will be collected in the study database but will not be reported in tables or listings. Any treatment emergent abnormal findings will be included in the AE listing. No formal statistical analyses of OHTE will be performed.

5 Changes to the Protocol Defined Statistical Analysis Plan

The repeated measures analysis of covariance described in section 4.3.2 to generate the bite force adjusted means and standard errors at each time point was added to create the figure requested by GSK.

List of Tables, Figures, and Listings

Tables

1. Premature discontinuation
2. Reason for Discontinuation (for subjects with premature discontinuation)
3. Analysis populations
4. Demographic characteristics
5. Baseline characteristics
6. ANOVA table for AOB₀₋₁₂
7. Adjusted means, standard errors, and 95% confidence intervals for AOB₀₋₁₂ by treatment.
8. Adjusted differences, standard errors, and 95% confidence intervals for AOB₀₋₁₂ between pairs of treatments.
9. ANOVA tables for AOB_{0-0.5}, AOB₀₋₁, AOB₀₋₃, AOB₀₋₆, and AOB₀₋₉
10. Adjusted means, standard errors, and 95% confidence intervals for AOB_{0-0.5}, AOB₀₋₁, AOB₀₋₃, AOB₀₋₆, and AOB₀₋₉ by treatment.
11. Adjusted differences, standard errors, and 95% confidence intervals for AOB_{0-0.5}, AOB₀₋₁, AOB₀₋₃, AOB₀₋₆, and AOB₀₋₉ between pairs of treatments.
12. Bite force adjusted means and standard errors over time by treatment.
13. Bite force, AUC, and AOB summary statistics by treatment and time
14. Number and percent of subjects with AE, Oral AE, TEAE, Product-related AE, Device Incidents, SAE

{note, tables 4-13 will be repeated as 4b-13b if the PP analysis is performed}

Listings

1. Protocol deviations.
2. Adverse events.
3. Medical device events.
4. Serious adverse events.

Figures

1. Line plot of bite force adjusted means over time with SE error bars by treatment.
2. Subject-level profile plots (connected scatter plots) of AOB_{0-0.5}, AOB₀₋₁, AOB₀₋₃, AOB₀₋₆, AOB₀₋₉, and AOB₀₋₁₂, with all treatments overlayed on the same figure. Plotted by subject.
3. Plot of adjusted differences with 95% confidence intervals for AOB₀₋₁₂ between pairs of treatments.

Rough draft of table shells

Table 1. Premature discontinuation

	N (%)
No	
Yes	
Total	

Table 2. Reason for Discontinuation (for subjects who did not complete study), check all that apply

	N
Subject Discontinued/Withdrew from the study due to COVID-19 pandemic	

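### AOB0-0.5 is exactly half the 30-minute gain in bite force: does the plan need an extra row, a footnote or a different plot?

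*SAP*

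**What the plan says.** SAP 4.3.1.1 states that bite force "will be recorded at hour 0 (baseline, pre-treatment) and at 0.5, 1, 3, 6, 9, and 12 hours post-treatment". The AUC is taken by the trapezoid rule on nominal times and divided by the window length, and the baseline bite is then subtracted. The SAP describes the result as being on the original bite-force scale and as "looking at the average amount of improved force over time by subtracting the baseline value". SAP 4.3.2 carries this to the shorter windows: "AOB for 0.5, 1, 3, 6 and 9 hours will be defined and analyzed in a similar manner as" AOB0-12. Protocol 12.3.2 says the same.

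The SAP's list of tables puts the between-treatment AOB differences for the five shorter windows in Table 11. Table 12 and Figure 1 give adjusted mean bite force at 0, 0.5, 1, 3, 6, 9 and 12 h by treatment. Of the model behind them SAP 4.3.2 says: "No statistical comparisons will be taken from this analysis". Table 13 is listed as "Bite force, AUC, and AOB summary statistics by treatment and time". The list of figures also has "Subject-level profile plots (connected scatter plots) of" the six AOB values, with all treatments overlaid for each subject.

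**The concern.** A reader who sees a 0.5 h row in pounds, in a SAP that says AOB is on the scale of the original readings, may take it as the gain at 30 minutes. It is half that gain. The time point is of interest: Protocol 2.2 cites earlier studies showing hold "as early as 30 mins after adhesive application", and the trial is meant to support product claims. Table 11 is also the only planned output giving an early treatment difference with a confidence interval, because no comparison is taken from the Table 12 model and Table 13 is descriptive.

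The subject-level plots raise a second worry. They join AOB values across windows whose weight on the baseline bite differs, so a line can rise from the first window to the second while hold is falling. At stake is how the early effect and its time course are read, not whether an adhesive is declared superior.

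**Working it through.** **Inputs.** Bite times are 0, 0.5, 1, 3, 6, 9 and 12 h, with hour 0 taken before the adhesive (SAP 4.3.1.1). AOB is AUC/T minus baseline, on nominal times (same section). The planned difference is 2.30 lb and the residual SD 2.83 lb, for 42 completers and 90% power (SAP 1.4). The documents give no figure for the shorter windows.

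**The plan's own figure.** SE = 2.83 × √(2/42) = 0.618 lb, and 2.30/0.618 = 3.72. Take 120 error degrees of freedom (assumed for a 4 × 4 crossover), the positive control tested at 5% and Dunnett's critical value of 2.24 for two comparisons. With one experimental adhesive effective, simulation gives 90.2%, which matches the stated 90%. This concerns AOB0-12 only and does not depend on how the shorter windows are reported.

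**The factor of one half.** Write B for the baseline bite and X for the 0.5 h bite.

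- AUC over 0 to 0.5 h = 0.5 × (B + X)/2 = 0.25B + 0.25X.
- Divided by 0.5: (B + X)/2.
- Minus B: (X − B)/2.

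Nominal times fix the weights. SAP 4.3.3 applies similar missing-value rules to the shorter windows; on that reading a missing 0.5 h bite makes AOB0-0.5 missing, so the factor never varies.

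**All windows.** The weight on B in AUC/T is 0.25/T. The last two columns are illustrations that use 2.30 lb as an assumed gain at 0.5 h. One holds it flat; the other lets it fall linearly to 1.15 lb at 12 h.

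| Window (h) | Weight on B | 1 − 0.25/T | AOB, flat (lb) | AOB, waning (lb) |
|---|---|---|---|---|
| 0–0.5 | 1/2 | 0.500 | 1.15 | 1.15 |
| 0–1 | 1/4 | 0.750 | 1.73 | 1.71 |
| 0–3 | 1/12 | 0.917 | 2.11 | 2.00 |
| 0–6 | 1/24 | 0.958 | 2.20 | 1.95 |
| 0–9 | 1/36 | 0.972 | 2.24 | 1.83 |
| 0–12 | 1/48 | 0.979 | 2.25 | 1.70 |

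**The first step of the plot.** With d for change from baseline, AOB0-1 = 0.5·d(0.5) + 0.25·d(1) and AOB0-0.5 = 0.5·d(0.5). The step between them is 0.25·d(1). It rises whenever the 1 h bite is above baseline, whatever happened between 30 minutes and 1 h.

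**Effect on the tests.** Doubling the outcome doubles the ANCOVA estimate, SE and confidence limits and leaves t unchanged. Fitting the SAP's model to one simulated crossover gave 0.9967 (SE 0.3124, t 3.19) for AOB0-0.5 and 1.9935 (SE 0.6248, t 3.19) for the 30-minute change, for the same contrast.

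**Is half the right size for a window average?** That depends on onset before 0.5 h, which is not measured. Let f be the mean gain over 0 to 0.5 h divided by the gain at 30 minutes, with a flat gain afterwards. The error in AOB0-0.5 is 0.5/f − 1, and in AOB0-1 it is 0.75/(0.5f + 0.5) − 1.

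| f | AOB0-0.5 | AOB0-1 |
|---|---|---|
| 1 | −50% | −25% |
| 0.75 | −33% | −14% |
| 0.5 (linear onset) | 0% | 0% |
| 0.25 | +100% | +20% |

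For AOB0-12 the error stays within about 2%. Protocol 2.4 describes a gradual process, "In the oral cavity, the cream absorbs water and the polymers hydrate", so immediate full hold is only one possibility.

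**The case for a change.** The strongest case for a change is that the misreading is easy and the remedy cheap: one row, one footnote and one figure, with every protocol endpoint kept. In a crossover the interval for a treatment difference cannot be rebuilt from the per-treatment standard errors in Table 12, and that model adjusts only for subject-level baseline. The profile plot does invite comparison across windows; in the waning illustration the last point (1.70 lb) lies above the first (1.15 lb) although the assumed gain has halved.

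The algebra stands, and so does the warning against reading AOB values from different windows as one curve. The need for a change does not.

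- The objectives (Protocol section 3, SAP 1.2) specify area over baseline up to each time, not an effect at 30 minutes, and Table 11 names its rows accordingly.
- The 30-minute difference and its interval need no new model: doubling the AOB0-0.5 row gives both.
- Waning would show in Figure 1, which plots bite force itself. The illustrated AOB profile also shows it, peaking at 2.00 lb at 3 h and falling about 15% to 1.70 lb.
- Overlaying the treatments allows the comparison within a window, which is valid. Replacing the plot would remove the only subject-level display of the declared endpoints.
- The table shells are headed as a rough draft, so a missing footnote there says little about the final output.

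One qualification: the equal p-value holds for the untransformed ANCOVA. Under the logarithm fallback in SAP 4.3.1.2, any offset added for negative AOB values would have to be scaled too.

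SAP 4.3.2 also points to AOB0-12 and Table 8 where Table 11 is evidently meant, and calls the profile plot Figure 3 where the list has Figure 2. These are clerical slips that the list of outputs resolves.

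**Conclusion.** No change is needed. AOB0-0.5 is half the 30-minute change by construction, and the weight on the baseline bite falls from 50% at 0.5 h to 2% at 12 h. Both facts follow exactly from the published definition. They alter the size at which a secondary result is shown, equally for all treatments within a window. They do not alter any planned contrast, p-value, decision rule, power or the primary result. Whether AOB0-0.5 understates or overstates the true average gain over the first half hour depends on unmeasured onset; with linear onset it is exact. The proposed row would repeat an existing test on a doubled scale, and a footnote or another plot is a presentation choice that can be made when the shells are finalised. The conclusion rests on use of nominal times, on the missing-value rule carrying over to the shorter windows, and on the untransformed ANCOVA. The 2.30 lb profiles are illustrations, not predictions.

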4.3.3 Handling of Missing Values/Censoring/Discontinuations

As described above for the calculation of $AOB_{0.12}$, missing readings will be imputed using linear interpolation between pre and post the missing values, if necessary. In the case of more than one missing value or if the 12-hour value is missing, $AOB_{0.12}$ will be set to missing. Similar rules will apply for the AOB calculations for 0.5, 1, 3, 6 and 9 hours. No other imputation of missing data will be considered.

The following will be considered violations that may lead to the exclusion of data from the PP population and hence PP analyses:

- Violation of inclusion or exclusion criteria at screening that may affect efficacy
- Violation of pre-treatment baseline bite force continuance criteria

- Treatment administration errors
- Use of prohibited treatment or medication before or during the study, which it is felt will affect the assessment of efficacy.

The above list is not exhaustive and all protocol violations will be assessed by the blinded GSK CH team members as to whether any subjects and /or data will be excluded from PP analysis as part of a Blind Data Review (BDR) Meeting prior to database lock. Any reasons for exclusion from an analysis population will be listed, if applicable.

Subjects with a protocol violation that is deemed to affect efficacy assessments in some, but not all, study periods will be part of the PP population, but their data will be excluded from the period(s) affected by the protocol violation for a PP analysis.

4.4 Analysis of Safety

All safety results will be produced from the Safety population.

4.4.1 Adverse Events and Serious Adverse Events

Adverse events (AEs) will be categorized as oral or non-oral by the examiner prior to database lock. AEs will be deemed to be treatment emergent if they occur after the first supervised use of the randomized treatment. No specific risks or anticipated adverse device effects are expected to be observed within this study, however all AEs and medical device incidents will be assessed to evaluate the tolerability and safety of the treatments. No formal statistical analyses of AEs will be performed. AEs will be listed in Listing 2. Serious Adverse Events (SAEs) will be listed in Listing 3.

4.4.2 Medical device events

The medical devices in this study are the supplied denture adhesive creams, the denture cleansing paste and the denture cleaning brushes. Medical device incidents involving an AE will be included in the AE listing. No formal statistical analyses of medical device events will be performed.

4.4.3 Oral Soft Tissue Examination

Oral soft tissue exam (OSTE) will be collected in the study database but will not be reported in tables or listings. Any treatment emergent abnormal findings will be included in the AE listing. No formal statistical analyses of OSTE will be performed.

4.4.4 Oral Hard Tissue Examination

Oral hard tissue exam (OHTE) will be collected in the study database but will not be reported in tables or listings. Any treatment emergent abnormal findings will be included in the AE listing. No formal statistical analyses of OHTE will be performed.

5 Changes to the Protocol Defined Statistical Analysis Plan

The repeated measures analysis of covariance described in section 4.3.2 to generate the bite force adjusted means and standard errors at each time point was added to create the figure requested by GSK.

List of Tables, Figures, and Listings

Tables

1. Premature discontinuation
2. Reason for Discontinuation (for subjects with premature discontinuation)
3. Analysis populations
4. Demographic characteristics
5. Baseline characteristics
6. ANOVA table for AOB₀₋₁₂
7. Adjusted means, standard errors, and 95% confidence intervals for AOB₀₋₁₂ by treatment.
8. Adjusted differences, standard errors, and 95% confidence intervals for AOB₀₋₁₂ between pairs of treatments.
9. ANOVA tables for AOB_{0-0.5}, AOB₀₋₁, AOB₀₋₃, AOB₀₋₆, and AOB₀₋₉
10. Adjusted means, standard errors, and 95% confidence intervals for AOB_{0-0.5}, AOB₀₋₁, AOB₀₋₃, AOB₀₋₆, and AOB₀₋₉ by treatment.
11. Adjusted differences, standard errors, and 95% confidence intervals for AOB_{0-0.5}, AOB₀₋₁, AOB₀₋₃, AOB₀₋₆, and AOB₀₋₉ between pairs of treatments.
12. Bite force adjusted means and standard errors over time by treatment.
13. Bite force, AUC, and AOB summary statistics by treatment and time
14. Number and percent of subjects with AE, Oral AE, TEAE, Product-related AE, Device Incidents, SAE

{note, tables 4-13 will be repeated as 4b-13b if the PP analysis is performed}

Listings

1. Protocol deviations.
2. Adverse events.
3. Medical device events.
4. Serious adverse events.

Figures

1. Line plot of bite force adjusted means over time with SE error bars by treatment.
2. Subject-level profile plots (connected scatter plots) of AOB_{0-0.5}, AOB₀₋₁, AOB₀₋₃, AOB₀₋₆, AOB₀₋₉, and AOB₀₋₁₂, with all treatments overlayed on the same figure. Plotted by subject.
3. Plot of adjusted differences with 95% confidence intervals for AOB₀₋₁₂ between pairs of treatments.

Rough draft of table shells

Table 1. Premature discontinuation

	N (%)
No	
Yes	
Total	

Table 2. Reason for Discontinuation (for subjects who did not complete study), check all that apply

	N
Subject Discontinued/Withdrew from the study due to COVID-19 pandemic	
Subject withdrew from the study at his or her own request	
Subject did not meet study criteria; specify the criterion or assessment not met	
Adverse event(s)	
The discretion of the investigator or sponsor for safety,	
Behavioral reasons	
Inability of the subject to comply with the protocol required schedule of study visits or procedures.	
Protocol violation that may impact the subject's safety	
Withdrawal of informed consent	
Subject lost to follow-up	
Pregnancy	
Death	

Table 3. Analysis populations

	Total	Experimental Denture Adhesive 1	Experimental Denture Adhesive 2	Super Poligrip Free Adhesive Cream	No Adhesive
	N	N	N	N	N
Safety					
MITT					
Reason for MITT exclusion					
PP					
Reason for PP exclusion					

Table 4. Demographic characteristics. MITT population.

	Total	Experiment al Denture Adhesive 1	Experiment al Denture Adhesive 2	Super Poligrip Free Adhesive Cream	No Adhesive
Age; N, Mean (SD), Median, Minimum-Maximum					
Sex					
Male; N (%)					
Female; N (%)					
Race (check all that apply)					
American Indian or Alaska Native; N (%)					
Asian; N (%)					
Black or African American; N (%)					
Native Hawaiian or Other Pacific Islander; N (%)					
White; N (%)					
Other; N (%)					
Ethnicity					
Hispanic or Latino; N (%)					
Not Hispanic or Latino; N (%)					

Table 4b. Demographic characteristics. PP population.

	Total	Experiment al Denture Adhesive 1	Experiment al Denture Adhesive 2	Super Poligrip Free Adhesive Cream	No Adhesive
Age; N, Mean (SD), Median, Minimum-Maximum					
Sex					
Male; N (%)					
Female; N (%)					
Race (check all that apply)					
American Indian or Alaska Native; N (%)					
Asian; N (%)					
Black or African American; N (%)					
Native Hawaiian or Other Pacific Islander; N (%)					
White; N (%)					
Other; N (%)					
Ethnicity					
Hispanic or Latino; N (%)					
Not Hispanic or Latino; N (%)					

Table 5. Baseline characteristics. MITT population.

	Total	Experiment al Denture Adhesive 1	Experiment al Denture Adhesive 2	Super Poligrip Free Adhesive Cream	No Adhesive
	N (%)	N (%)	N (%)	N (%)	N (%)
Denture bearing tissue evaluation					
Ridge shape					
Flat					
V-shaped					
U-shaped					
Tissue Resiliency					
Flabby					
Resilient					
Firm					
Border Tissue Attachment					
Low					
Medium					
High					
Well-made Assessment					
Has this denture clinically acceptable vertical dimension, freeway space, horizontal occlusal relationships and border extensions?					
Acceptable					
Unacceptable					
Has this denture clinically acceptable contour and finish?					
Acceptable					
Unacceptable					
Has this denture clinically acceptable porosity, tissue surfaces, polished surfaces, color and thickness?					
Acceptable					
Unacceptable					

Table 5b. Baseline characteristics. PP population.

	Total	Experiment al Denture Adhesive 1	Experiment al Denture Adhesive 2	Super Poligrip Free Adhesive Cream	No Adhesive
	N (%)	N (%)	N (%)	N (%)	N (%)
Denture bearing tissue evaluation					
Ridge shape					
Flat					
V-shaped					
Shaped between U & V					
U-shaped					
Tissue Resiliency					
Flabby					
Resilient					
Firm					
Border Tissue Attachment					
Low					
Medium					
High					
Well-made Assessment					
Has this denture clinically acceptable vertical dimension, freeway space, horizontal occlusal relationships and border extensions?					
Acceptable					
Unacceptable					
Has this denture clinically acceptable contour and finish?					
Acceptable					
Unacceptable					
Has this denture clinically acceptable porosity, tissue surfaces, polished surfaces, color and thickness?					
Acceptable					
Unacceptable					

Table 6. ANOVA table for AOB₀₋₁₂. MITT population.

	Num DF	Den DF	F-value	p-value
Treatment				
Period				
Subject-level baseline				
Period level baseline minus subject level baseline				

Table 6b. ANOVA table for AOB₀₋₁₂. PP population.

	Num DF	Den DF	F-value	p-value
Treatment				
Period				
Subject-level baseline				
Period level baseline minus subject level baseline				

Table 7. Adjusted means, standard errors, and 95% confidence intervals for AOB_{0-12} (lbs) by treatment. MITT population.

		AOB_{0-12} (lbs)			
	N	LS Mean	SE	95% LCL	95% UCL
Experimental Denture Adhesive 1					
Experimental Denture Adhesive 2					
Super Poligrip Free Adhesive Cream					
No Adhesive					

Table 7b. Adjusted means, standard errors, and 95% confidence intervals for AOB_{0-12} (lbs) by treatment. PP population.

		AOB_{0-12} (lbs)			
	N	LS Mean	SE	95% LCL	95% UCL
Experimental Denture Adhesive 1					
Experimental Denture Adhesive 2					
Super Poligrip Free Adhesive Cream					
No Adhesive					

Table 8. Adjusted differences, standard errors, and 95% confidence intervals for AOB_{0-12} (lbs) between pairs of treatments. MITT population

		AOB_{0-12} (lbs)				
	N/N	Difference	SE	p-value	95% LCL	95% UCL
Super Poligrip Free Adhesive Cream vs. No Adhesive						
Experimental Denture Adhesive 1 vs. No Adhesive						
Experimental Denture Adhesive 2 vs. No Adhesive						

Table 8b. Adjusted differences, standard errors, and 95% confidence intervals for AOB_{0-12} (lbs) between pairs of treatments. PP population

		AOB_{0-12} (lbs)				
	N/N	Difference	SE	p-value	95% LCL	95% UCL
Super Poligrip Free Adhesive Cream vs. No Adhesive						
Experimental Denture Adhesive 1 vs. No Adhesive						
Experimental Denture Adhesive 2 vs. No Adhesive						

Table 9. ANOVA table for AOB_{0.5}, AOB_{0.1}, AOB_{0.3}, AOB_{0.6}, and AOB_{0.9}. MITT population.

		Num DF	Den DF	F-value	p-value
AOB _{0.5}	Treatment				
	Period				
	Subject-level baseline				
	Period level baseline minus subject level baseline				
AOB _{0.1}	Treatment				
	Period				
	Subject-level baseline				
	Period level baseline minus subject level baseline				
AOB _{0.3}	Treatment				
	Period				
	Subject-level baseline				
	Period level baseline minus subject level baseline				
AOB _{0.6}	Treatment				
	Period				
	Subject-level baseline				
	Period level baseline minus subject level baseline				
AOB _{0.9}	Treatment				
	Period				
	Subject-level baseline				
	Period level baseline minus subject level baseline				

Table 9b. ANOVA table for AOB_{0.5}, AOB_{0.1}, AOB_{0.3}, AOB_{0.6}, and AOB_{0.9}. PP population.

		Num DF	Den DF	F-value	p-value
AOB _{0.5}	Treatment				
	Period				
	Subject-level baseline				
	Period level baseline minus subject level baseline				
AOB _{0.1}	Treatment				
	Period				
	Subject-level baseline				
	Period level baseline minus subject level baseline				
AOB _{0.3}	Treatment				
	Period				
	Subject-level baseline				
	Period level baseline minus subject level baseline				
AOB _{0.6}	Treatment				
	Period				
	Subject-level baseline				
	Period level baseline minus subject level baseline				
AOB _{0.9}	Treatment				
	Period				
	Subject-level baseline				
	Period level baseline minus subject level baseline				

Table 10. Adjusted means, standard errors, and 95% confidence intervals for $AOB_{0.5}$, $AOB_{0.1}$, $AOB_{0.3}$, $AOB_{0.6}$, and $AOB_{0.9}$ by treatment. MITT population.

		N	LS Mean	SE	95% LCL	95% UCL
$AOB_{0.5}$ (lbs)	Experimental Denture Adhesive 1					
	Experimental Denture Adhesive 2					
	Super Poligrip Free Adhesive Cream					
	No Adhesive					
$AOB_{0.1}$ (lbs)	Experimental Denture Adhesive 1					
	Experimental Denture Adhesive 2					
	Super Poligrip Free Adhesive Cream					
	No Adhesive					
$AOB_{0.3}$ (lbs)	Experimental Denture Adhesive 1					
	Experimental Denture Adhesive 2					
	Super Poligrip Free Adhesive Cream					
	No Adhesive					
$AOB_{0.6}$ (lbs)	Experimental Denture Adhesive 1					
	Experimental Denture Adhesive 2					
	Super Poligrip Free Adhesive Cream					
	No Adhesive					

AOB _{0.9} (lbs)	Experimental Denture Adhesive 1					
	Experimental Denture Adhesive 2					
	Super Poligrip Free Adhesive Cream					
	No Adhesive					

Table 10b. Adjusted means, standard errors, and 95% confidence intervals for $AOB_{0.5}$, $AOB_{0.1}$, $AOB_{0.3}$, $AOB_{0.6}$, and $AOB_{0.9}$ by treatment. PP population.

		N	LS Mean	SE	95% LCL	95% UCL
$AOB_{0.5}$ (lbs)	Experimental Denture Adhesive 1					
	Experimental Denture Adhesive 2					
	Super Poligrip Free Adhesive Cream					
	No Adhesive					
$AOB_{0.1}$ (lbs)	Experimental Denture Adhesive 1					
	Experimental Denture Adhesive 2					
	Super Poligrip Free Adhesive Cream					
	No Adhesive					
$AOB_{0.3}$ (lbs)	Experimental Denture Adhesive 1					
	Experimental Denture Adhesive 2					
	Super Poligrip Free Adhesive Cream					
	No Adhesive					
$AOB_{0.6}$ (lbs)	Experimental Denture Adhesive 1					
	Experimental Denture Adhesive 2					
	Super Poligrip Free Adhesive Cream					
	No Adhesive					

AOB ₀₋₉ (lbs)	Experimental Denture Adhesive 1					
	Experimental Denture Adhesive 2					
	Super Poligrip Free Adhesive Cream					
	No Adhesive					

Table 11. Adjusted differences, standard errors, and 95% confidence intervals for $AOB_{0.5}$, $AOB_{0.1}$, $AOB_{0.3}$, $AOB_{0.6}$, and $AOB_{0.9}$ between pairs of treatments. MITT population

		N/N	Difference	SE	p-value	95% LCL	95% UCL
$AOB_{0.5}$ (lbs)	Super Poligrip Free Adhesive Cream vs. No Adhesive						
	Experimental Denture Adhesive 1 vs. No Adhesive						
	Experimental Denture Adhesive 2 vs. No Adhesive						
$AOB_{0.1}$ (lbs)	Super Poligrip Free Adhesive Cream vs. No Adhesive						
	Experimental Denture Adhesive 1 vs. No Adhesive						
	Experimental Denture Adhesive 2 vs. No Adhesive						
$AOB_{0.3}$ (lbs)	Super Poligrip Free Adhesive Cream vs. No Adhesive						
	Experimental Denture Adhesive 1 vs. No Adhesive						
	Experimental Denture Adhesive 2 vs. No Adhesive						
$AOB_{0.6}$ (lbs)	Super Poligrip Free Adhesive Cream vs. No Adhesive						
	Experimental Denture Adhesive 1 vs. No Adhesive						
	Experimental Denture Adhesive 2 vs. No Adhesive						
$AOB_{0.9}$ (lbs)	Super Poligrip Free Adhesive Cream vs. No Adhesive						

	Experimental Denture Adhesive 1 vs. No Adhesive						
	Experimental Denture Adhesive 2 vs. No Adhesive						

Table 11b. Adjusted differences, standard errors, and 95% confidence intervals for $AOB_{0.5}$, $AOB_{0.1}$, $AOB_{0.3}$, $AOB_{0.6}$, and $AOB_{0.9}$ between pairs of treatments. PP population

		N/N	Difference	SE	p-value	95% LCL	95% UCL
$AOB_{0.5}$ (lbs)	Super Poligrip Free Adhesive Cream vs. No Adhesive						
	Experimental Denture Adhesive 1 vs. No Adhesive						
	Experimental Denture Adhesive 2 vs. No Adhesive						
$AOB_{0.1}$ (lbs)	Super Poligrip Free Adhesive Cream vs. No Adhesive						
	Experimental Denture Adhesive 1 vs. No Adhesive						
	Experimental Denture Adhesive 2 vs. No Adhesive						
$AOB_{0.3}$ (lbs)	Super Poligrip Free Adhesive Cream vs. No Adhesive						
	Experimental Denture Adhesive 1 vs. No Adhesive						
	Experimental Denture Adhesive 2 vs. No Adhesive						
$AOB_{0.6}$ (lbs)	Super Poligrip Free Adhesive Cream vs. No Adhesive						
	Experimental Denture Adhesive 1 vs. No Adhesive						
	Experimental Denture Adhesive 2 vs. No Adhesive						
$AOB_{0.9}$ (lbs)	Super Poligrip Free Adhesive Cream vs. No Adhesive						

	Experimental Denture Adhesive 1 vs. No Adhesive						
	Experimental Denture Adhesive 2 vs. No Adhesive						

Table 12. Bite force (lbs) adjusted means and standard errors over time by treatment. MITT population.

		Bite Force (lbs)										
		Experimental Denture Adhesive 1			Experimental Denture Adhesive 2			Super Poligrip Free Adhesive Cream			No Adhesive	
Time	N	Mean	SE	N	Mean	SE	N	Mean	SE	N	Mean	SE
0												
0.5												
1												
3												
6												
9												
12												

Table 12b. Bite force (lbs) adjusted means and standard errors over time by treatment. PP population.

		Bite Force (lbs)										
		Experimental Denture Adhesive 1			Experimental Denture Adhesive 2			Super Poligrip Free Adhesive Cream			No Adhesive	
Time	N	Mean	SE	N	Mean	SE	N	Mean	SE	N	Mean	SE
0												
0.5												
1												
3												
6												
9												
12												

Table 13a. Bite force (lbs), AUC (lbs), and AOB (lbs) summary statistics by treatment and time.
 MITT population.

		N	Mean	SD	SE	Median	Min	Max
Bite Force (lbs)								
Experimental Denture Adhesive 1	BF ₀							
	BF _{0.5}							
	BF ₁							
	BF ₃							
	BF ₆							
	BF ₉							
	BF ₁₂							
Experimental Denture Adhesive 2	BF ₀							
	BF _{0.5}							
	BF ₁							
	BF ₃							
	BF ₆							
	BF ₉							
	BF ₁₂							
Super Poligrip Free Adhesive Cream	BF ₀							
	BF _{0.5}							
	BF ₁							
	BF ₃							
	BF ₆							
	BF ₉							
	BF ₁₂							
No Adhesive	BF ₀							
	BF _{0.5}							
	BF ₁							
	BF ₃							
	BF ₆							
	BF ₉							
	BF ₁₂							
AUC (lbs)								

Experimental Denture Adhesive 1	AUC _{0-0.5}							
	AUC ₀₋₁							
	AUC ₀₋₃							
	AUC ₀₋₆							
	AUC ₀₋₉							
	AUC ₀₋₁₂							
Experimental Denture Adhesive 2	AUC _{0-0.5}							
	AUC ₀₋₁							
	AUC ₀₋₃							
	AUC ₀₋₆							
	AUC ₀₋₉							
	AUC ₀₋₁₂							
Super Poligrip Free Adhesive Cream	AUC _{0-0.5}							
	AUC ₀₋₁							
	AUC ₀₋₃							
	AUC ₀₋₆							
	AUC ₀₋₉							
	AUC ₀₋₁₂							
No Adhesive	AUC _{0-0.5}							
	AUC ₀₋₁							
	AUC ₀₋₃							
	AUC ₀₋₆							
	AUC ₀₋₉							
	AUC ₀₋₁₂							
AOB (lbs)								
Experimental Denture Adhesive 1	AOB _{0-0.5}							
	AOB ₀₋₁							
	AOB ₀₋₃							

	AOB ₀₋₆							
	AOB ₀₋₉							
	AOB ₀₋₁₂							
Experimental Denture Adhesive 2	AOB _{0-0.5}							
	AOB ₀₋₁							
	AOB ₀₋₃							
	AOB ₀₋₆							
	AOB ₀₋₉							
	AOB ₀₋₁₂							
Super Poligrip Free Adhesive Cream	AOB _{0-0.5}							
	AOB ₀₋₁							
	AOB ₀₋₃							
	AOB ₀₋₆							
	AOB ₀₋₉							
	AOB ₀₋₁₂							
No Adhesive	AOB _{0-0.5}							
	AOB ₀₋₁							
	AOB ₀₋₃							
	AOB ₀₋₆							
	AOB ₀₋₉							
	AOB ₀₋₁₂							

Table 13b. Bite force (lbs), AUC (lbs), and AOB (lbs) summary statistics by treatment and time.
 PP population.

		N	Mean	SD	SE	Median	Min	Max
Bite Force (lbs)								
Experimental Denture Adhesive 1	BF ₀							
	BF _{0.5}							
	BF ₁							
	BF ₃							
	BF ₆							
	BF ₉							
	BF ₁₂							
Experimental Denture Adhesive 2	BF ₀							
	BF _{0.5}							
	BF ₁							
	BF ₃							
	BF ₆							
	BF ₉							
	BF ₁₂							
Super Poligrip Free Adhesive Cream	BF ₀							
	BF _{0.5}							
	BF ₁							
	BF ₃							
	BF ₆							
	BF ₉							
	BF ₁₂							
No Adhesive	BF ₀							
	BF _{0.5}							
	BF ₁							
	BF ₃							
	BF ₆							
	BF ₉							
	BF ₁₂							
AUC (lbs)								

Experimental Denture Adhesive 1	AUC _{0-0.5}							
	AUC ₀₋₁							
	AUC ₀₋₃							
	AUC ₀₋₆							
	AUC ₀₋₉							
	AUC ₀₋₁₂							
Experimental Denture Adhesive 2	AUC _{0-0.5}							
	AUC ₀₋₁							
	AUC ₀₋₃							
	AUC ₀₋₆							
	AUC ₀₋₉							
	AUC ₀₋₁₂							
Super Poligrip Free Adhesive Cream	AUC _{0-0.5}							
	AUC ₀₋₁							
	AUC ₀₋₃							
	AUC ₀₋₆							
	AUC ₀₋₉							
	AUC ₀₋₁₂							
No Adhesive	AUC _{0-0.5}							
	AUC ₀₋₁							
	AUC ₀₋₃							
	AUC ₀₋₆							
	AUC ₀₋₉							
	AUC ₀₋₁₂							
AOB (lbs)								
Experimental Denture Adhesive 1	AOB _{0-0.5}							
	AOB ₀₋₁							
	AOB ₀₋₃							

	AOB ₀₋₆							
	AOB ₀₋₉							
	AOB ₀₋₁₂							
Experimental Denture Adhesive 2	AOB _{0-0.5}							
	AOB ₀₋₁							
	AOB ₀₋₃							
	AOB ₀₋₆							
	AOB ₀₋₉							
	AOB ₀₋₁₂							
Super Poligrip Free Adhesive Cream	AOB _{0-0.5}							
	AOB ₀₋₁							
	AOB ₀₋₃							
	AOB ₀₋₆							
	AOB ₀₋₉							
	AOB ₀₋₁₂							
No Adhesive	AOB _{0-0.5}							
	AOB ₀₋₁							
	AOB ₀₋₃							
	AOB ₀₋₆							
	AOB ₀₋₉							
	AOB ₀₋₁₂							

Table 14. AE, TEAE, Product-related AE, Medical device related AE, SAE, Medical device event

	Total
AE; N (%)	
Oral AE; N (%)	
TEAE; N (%)	
Product-related AE; N (%)	
Medical Device related AE; N (%)	
SAE; N (%)	
Medical Device Event; N (%)	

Listing 1. Protocol deviations

ID	Deviation date	Visit(s) affected	Nature of deviation	Missed applications	Additional applications	Other	Description	Comments	Exclusion from PP

Listing 2. Adverse events.

ID	Age	Sex	Race	AE	Start date	Stop date	COVI D-related	Serious	Product-related	Oral	TEAE	Product Action	Outcome	SAE	Ongoing	Expected	Frequency	Discontinue	Comment

Listing 3. Medical device events.

ID	Device type	Incident type	Incident type other	Start date	Stop date	Outcome	Treatment given	Corrective action	AE	Device cause AE	Subject Withdrawn	Device available	Device details

Listing 4. Serious adverse events.

{same as Listing 2, subset to SAEs}
